## OBJECTIVE

The perforator flap is a new improvement in reconstructive microsurgery that is increasingly gaining popularity in many different reconstructive applications to breast, torso, and extremities [Saint-Cyr 2009; Geddes 2003]. Because there is considerable inter-patient variation in the number, size, and position of perforator vessels, success of perforator flap surgery relies on state-of-the-art preoperative planning based on detailed understanding of the three-dimensional (3D) structure of the associated vasculature. Currently, computed tomography angiography (CTA) is the method-of-choice for preoperative vascular imaging in breast reconstruction surgeries. While CTA is capable of generating excellent anatomical details of perforator vessels, patients are also exposed to additional risks associated with the use of ionizing radiation and iodinated contrast agents. Magnetic resonance angiography (MRA) using intrinsic contrast mechanisms (without the use of any external contrast medium), such as velocity-encoded phase contrast, can generate accurate, high-resolution 3D vasculature maps without the risks associated with CTA. Therefore, non-contrast MRA is a more desirable alternative to CTA in preoperative planning of flap surgeries.

The overall objective of this pilot study is to develop and optimize preoperative MRA imaging protocols for various perforators commonly used in flap surgery with phantom and healthy volunteers, and to obtain clinical validation of the optimized protocols with a group of patients receiving flap surgery at the OSU Wexner Medical Center. Data obtained in this study may also serve as the basis for statistical planning of future clinical trials.

Based on our previous experience with other magnetic resonance imaging (MRI) techniques, we hypothesize that optimal MRA images can only be obtained with a carefully selected combination of imaging hardware, acquisition, and postprocessing factors. The main objective of this pilot study is to

determine this optimal combination through the comparison of image quality between different combinations.

The secondary objective of this pilot study is to evaluate, both qualitatively and quantitatively (for details see below), the quality of the optimized MRA images and compare them with clinical CTA images. Our hypothesis is that the quality of the optimized MRA images is at least comparable to that of the CTA images. The quantitative measurements obtained from this pilot population will also serve as the preliminary data for future studies and be used in statistical calculations that determine their study population.

## BACKGROUND AND RATIONALE

### Perforator Flap Surgery

Although the history of flap surgery – transplantation of tissue carrying its own blood supply – can be traced back to around 600 B.C. according to record in *Sushruta Samita*, the importance of adequate blood supply to flap survival is not fully demonstrated until Milton's work in 1970 [Milton 1970]. With this understanding, musculocutaneous flap surgery became popular in late 1970s due to the reliable blood supply of muscles [Ger 1966; Orticochea 1972]. However, removal of bulk muscular tissue from the donor site may have a negative impact on its structural and functional integrity. In an evaluation of the long-term abdominal consequences of Transverse Rectus Abdominis Musculocutaneous (TRAM) flap surgery, Mizgala et al. reported decreased abdominal strength and exercise ability in 46% and 25% of 150 patients, respectively. Other undesirable side-effects include asymptomatic diffuse bulges through the fascial harvest site, abdominal laxity, and increased back pain [Mizgala 1994].

In 1989, the musculocutaneous perforator flap was introduced by Koshima and Soeda [Koshima 1989]. In this procedure, the major perforator arteries feeding the donor site are carefully dissected from bulk muscle and transplanted to the recipient site with the attached skin and subcutaneous fat. By preserving the passive muscle carriers at the donor site, the plastic surgeons get more versatility in surgery design, and the patient experiences less donor site morbidity than in a musculocutaneous flap procedure. A number of studies have been conducted to compare the outcomes of perforator and musculocutaneous flap procedures, predominantly between the Deep Inferior Epigastric Perforator (DIEP) flap and TRAM flap used in post-mastectomy breast reconstruction. These studies demonstrated that TRAM flap patients have statistically significant weakness of abdominal and back muscles compared with patients receiving DIEP flap surgery [Blondeel 1997; Futter 2000]. DIEP flap patients were also reported to have slightly shorter hospital stay and lower risk for abdominal wall hernia than pedicled TRAM flap patients [Garvey 2006]. Recently, Man and colleagues conducted a meta-analysis of DIEP and free TRAM data published in English-language journals up to April, 2007. The results of this meta-analysis confirmed that donor-site morbidity is generally lower in DIEP patients [Man 2009].

## Commonly Used Perforator Flaps

The perforator flap method was quickly applied to various branches of plastic surgery soon after its introduction [Saint-Cyr 2009; Geddes 2003]. Currently, the most commonly used perforator flaps include:

- Deep Inferior Epigastric Perforator (DIEP) flap: This is the original perforator flap described by Koshima and Soeda. The perforators used in this procedure are branched from the deep inferior epigastric artery, and harvested from the rectus abdominis muscle. The primary application of DIEP flap is in post-mastectomy breast reconstruction. It has also been used in reconstruction of defects in lower limbs and head and neck.
- Thoracodorsal Artery Perforator (TDAP) flap: The perforators used in this procedure are branched from the thoracodorsal artery, and harvested from the latissimus dorsi muscle. The TAP flap is a highly versatile procedure because of the long pedicle and large cutaneous area in this region. It has been used for the reconstruction of defects in head and neck, torso, and extremities. Application in breast reconstruction has also been reported.
- Superior/Inferior Gluteal Artery Perforator (SGAP/IGAP) flap: The perforators used in these procedures are branched from the superior/inferior gluteal artery, and harvested from the gluteus maximus muscle. The gluteal artery perforator flaps are used as an alternative to abdominal flaps in breast reconstruction when abdominal flaps are considered unsuitable for the patient.
- AnteroLateral Thigh (ALT) flap: The perforators used in this procedure are branched from the descending branch of the lateral circumflex femoral artery, and harvested from the vastus lateralis muscle. The ALT flap is a popular procedure for head and neck reconstructive surgery in the Asian population.

## Preoperative Planning for Perforator Flaps

Because there is a large inter-patient variation in the number, size, and position of perforator vessels [Hallock 2001], careful, personalized preoperative planning for every patient is of essential importance to the success of perforator flap surgery. Initially, this was done with acoustic Doppler ultrasound sonography and color duplex sonography [Hallock 1994; Giunta 2000]. In this examination, a Doppler probe is scanned over the skin of the donor site. Pulsating Doppler signals mark out the presence of flow in blood vessels. The point with the loudest signal is identified as the position of the perforator. A major problem of the Doppler ultrasound technique is that its signal strength is only dependent on one component of the relative motion speed along the direction of the ultrasound beam. Therefore, a small vessel along the ultrasound beam direction may generate stronger signals than a large perforator running along an oblique direction. This technique thus tends to detect many small vessels that are not suitable for perforator flap surgery and yield a high proportion of false positive results. Giunta and colleagues reported that 47.6% of 271 “perforators” detected with acoustic Doppler ultrasound sonography were actually not dissected intraoperatively in DIEP and SGAP flap surgeries [Giunta 2000]. Yu et al. had similar findings for the ALT flap procedure, and observed that the accuracy of Doppler examination decreases with increasing body mass index [Yu 2006]. Other minor disadvantages of

Doppler ultrasound sonography include suboptimal presentation of images to the surgeons and the lack of the capability to reconstruct a 3D tomographic volume.

Several other non-invasive imaging modalities, including near-infrared fluorescence angiography [Matsui 2010], CTA [Karunanity 2011; Rozen 2008a], and contrast enhanced MRA (CE-MRA) [Greenspun 2010; Neil-Dwyer 2009], have been evaluated in efforts of finding a better planning tool for perforator flap surgeries. Currently, the plastic surgery community considers CTA as the method-of-choice for preoperative planning in breast reconstruction surgeries using DIEP or SGAP/IGAP. Despite some recent critics on inaccuracy in perforator caliber measurement [Cina 2010], CTA has substantial advantages in several aspects compared with the traditional Doppler techniques: It generates less false positive results and is more sensitive than Doppler ultrasound in detecting perforators [Rozen 2008b]. It is also superior in visualizing the intramuscular course of the perforators and the superficial subcutaneous vascular network [Cina 2010]. CTA images can be rendered as a 3D volume for comprehensive preoperative planning, and saved for intraoperative display. This helps to substantially improve planning quality and reduce operative time. Acosta and colleagues reported that incorporating CTA into their workflow has led to a mean reduction of 90 minutes to the operative time of DIEP flap breast reconstruction [Acosta 2011].

However, all these advantages come with a price of additional health risk to patients: The ionizing radiation used in Computed Tomography is known to have carcinogenic, teratogenic and mutagenic effects [Bushberg 2001]. Although the radiation dose of a single abdominal CTA is moderate (Phillips et al. estimated the average effective dose to be 6 mSv [Phillips 2008]), a large proportion of the patient population are also subject to repetitive scans and/or radiotherapy due to their medical conditions that raise the need for a perforator flap surgery. For those patients, it is important to reduce any unnecessary exposure to ionizing radiation to minimize the accumulative dose they receive. Moreover, in order to get high quality CT images of small perforators, intravenous injection of iodinated contrast agents is required. Iodinated contrast agents can induce anaphylactic reactions in a dose-independent and unpredictable way. The overall adverse reaction rate (including the anaphylactic reactions and chemotoxicity of the contrast agents) is estimated to be 4% to 12% for ionic contrast agents and 1% to 3% to nonionic contrast agents [Cochran 2005]. All of these adverse effects sum up to a non-negligible health risk to patients using CTA in their perforator flap surgery planning. Therefore, we propose this pilot study to investigate the use of non-contrast, non-ionizing-radiation MRA techniques as a better alternative to CTA in preoperative planning for perforator flap surgeries.

### **Non-contrast MRA for Perforator Imaging**

Various non-contrast MRA methods have been developed using different intrinsic contrast mechanisms [Bernstein 2004]. After careful review of the basic physical principles behind these methods, we decided that the following portfolio is the most suitable for visualizing perforators and subcutaneous vascular network:

- Phase contrast MRA uses flow-encoding gradients to create image contrast between moving and stationary magnetizations [Moran 1982]. The flow-encoding gradients can be applied in

three orthogonal directions so that blood flows in all directions can be simultaneously visualized in the same image. This feature is particularly important in imaging DIEP and TAP because blood in these vessels flows in opposite direction to aorta blood that supplies them, which makes flow direction sensitive techniques like time-of-flight (TOF) MRA unsuitable. Moreover, phase contrast MRA can be acquired as a 3D volume for better SNR to support the high spatial resolution needed for the visualization of small perforators. This technique will be used to obtain an overview of the perforators and their connections to their feeding vessels and subcutaneous vascular network.

- Sometimes a plastic surgeon also wants to know the anatomy of the subcutaneous vascular network. This information can be used to help him make surgical decisions that minimize the impact to the donor site. Images of the subcutaneous vascular network can be obtained with superb spatial resolution (300-500  $\mu\text{m}$ ) using the fat-water differences in their resonance frequencies (i.e. chemical shift contrast) [Wang 1998] or spin-lattice relaxation rates (i.e. T1 contrast) [Delfaut 1999].
- The capability of differentiating arteries and veins is a major advantage of color Doppler ultrasound over CTA. We would like to explore if non-contrast MRA techniques can provide a comprehensive preoperative imaging solution that combines the advantages of CTA and color Doppler ultrasound. Therefore, we also plan to acquire an MR venogram with a susceptibility weighted imaging (SWI) sequence, which is particularly sensitive to the paramagnetic deoxyhemoglobin rich in venous blood [Haacke 2010].

According to the result of a simulated phantom experiment on the MR scanner that will be used in this pilot study, it takes 20-30 minutes to acquire this protocol, along with a short localizer and a typical abdominal anatomical sequence. This is substantially shorter than a typical clinical MRI scan, which takes up to 60 minutes.

## **RESEARCH DESIGN AND METHODS**

### **Design Overview**

In this study, we plans to enroll 25 evaluable volunteers for the development and optimization of perforator imaging protocols, and 50 evaluable clinical patients receiving flap procedures at OSUMC for the clinical validation of the optimized protocol. Both genders will be included. Pediatric patients will be excluded. All subjects will be non-invasively imaged with a set of angiographic and anatomical MRI techniques. No extrinsic MR contrast agent will be injected. Clinical patients' MRI images will be evaluated independently by radiologists and plastic surgeons, and compared to clinical CTA images. The protocol will be performed in accordance with the Ohio State University Institutional Review Board regulations.

### **Recruitment**

Clinical patients will be recruited from the investigators' clinical practices. Once a potential study subject is identified by a recruiting physician, the study PI will be notified for the determination of eligibility.

Volunteers will be recruited through electronic advertisements posted on OSU websites, paper advertisement posted in OSU campus (see the attached brochure), and word of mouth.

All participants will be screened prior to entering the MRI environment.

### **Subject Selection Criteria**

Study subjects will be recruited for the MRI exam according to the following inclusion criteria:

- Greater than or equal to 18 years at time of enrollment.
- Able to provide informed consent.
- Able to lie in both prone and supine positions for at least 30 minutes.
- The clinical patients need to have a flap procedure scheduled at the Ohio State University Medical Center within the next 24 months.

If any of the following are applicable to a volunteer subject then he/she will be excluded from this study for the sake of their own safety:

- Use of an IUD (intrauterine device) or medicine patch
- Subjects with any type of activatable implants (e.g. cardiac pacemakers, deep brain stimulators, spinal cord stimulators, cochlear implants, electronic infusion pumps, etc.).
- Subjects with any type of metallic implants or foreign objects in torso region (e.g. cardiac stents, surgical clips, shrapnel fragments from war wounds, etc.).
- Metal works and machinists (who may have metallic fragments in the near eyes).
- Severe auto accident victims.
- Subjects with permanent tattoos that may contain metallic coloring.
- Subjects with previous history of perforator flap surgery.
- Subjects who cannot communicate with the researcher for any reason.
- Claustrophobia.

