- If volunteers have a metal implant or foreign object in your body, the object could be displaced by the magnetic field. There can be increased heating near metal structures. If volunteers have any implants in their body, they will inform the researcher conducting this study, and they will not be eligible to participate in this study.
- Volunteers will be placed in the long tube of the MRI system. Some volunteers may have a claustrophobic reaction (uneasiness at being in a confined space). If this happens, volunteers will be asked if they wish to continue, or if they would like to terminate the study.
- Volunteers will hear loud thumping sounds that may be annoying. Volunteers will be supplied with earplugs that you should wear while they are in the MRI system.
- Exposure to the rapidly changing electrical fields could cause twitching of your muscles. This effect is usually temporary.

- When volunteers close their eyes, they might see tiny light flashes similar to those that occur when they rub their eyes in the dark. This has no known harmful effects.
- All these listed effects are transient, that is, seeing light flashes, metallic taste and muscle twitching will end once exposure to the MRI fields is ended. Based on this, effects of repeated MRI studies are not expected, however, long-term effects are not known at this time.

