## **Compensation**

All patient subjects will be compensated with a \$40 gift card at the Wright Center of Innovation for each research MRI scan they participate. Those who come to the Wright Center but are not able to complete the research MRI scan (due to unforeseen medical reasons or equipment breakdown) will be still compensated. All patient subjects will be asked to sign a form as proof of receiving payment. By law, payments to subjects are considered taxable income.

Volunteer subjects will not be compensated for their participation.

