## **Adverse Events**

No invasive procedure or extrinsic agent will be applied or delivered to the subjects participating in this study. All MRI sequences used in this study will be identical to those used in daily clinical standard of care practices. Therefore, the health risk to the participants will not be greater than that of patients receiving a standard care diagnostic MRI examination.

The United States Food and Drug Administration (FDA) classified MRI up to 8.0 Tesla as non-significant risk. Potential risks include:

- 1) Excessive heat deposition in tissue due to high specific absorption rate (SAR);
- 2) Undesired neural stimulation due to fast switching of magnetic field gradients;
- 3) Malfunction of functional implants whose operation can be interfered by the RF field or the magnetic field gradients;
- 4) Temporary or permanent hear losses due to loud acoustic noises.

In this study, these potential risks are minimized:

- 1) The Philips 3.0 Tesla MRI system has both hardware and software limits on the maximum SAR level to less than or equal to 4.0 W/kg. This is the FDA approved limit. Excessive heat deposition may happen on the surface or near the tip of metallic objects embedded in body. However, these subjects will be excluded from participating this study by the use of the MRI Safety Screening Form;

- 2) The Philips 3.0 Tesla MRI system operates within the FDA guidelines regarding time varying magnetic field gradients;
- 3) All MRI sequence to be used are included in the FDA released clinical system sequence packages;
- 4) According to our exclusion criteria, all subjects with any type of activatable implants will be excluded from participating this study;
- 5) Dual ear protections (i.e. ear plugs and headphones) will be provided to all subjects participating in this study. With these protections in place, the scanner noise level will be under the FDA limit for sound (140 dB peak or 99 dB average).

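### The eligibility list excludes passive metal only in the torso, while two other sections of the protocol exclude it with no limit on body site

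*Protocol*

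**What the plan says.** Three sections of the Protocol deal with metal in the body at the 3 Tesla scan.

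- **Subject Selection Criteria.** One of the nine exclusion items covers passive metal: "Subjects with any type of metallic implants or foreign objects in torso region". It is the only item of the nine with a torso limit. Activatable implants are a separate item with no site limit. The list opens with "If any of the following are applicable to a volunteer subject then he/she will be excluded from this study".
- **General Magnetic Resonance Imaging Procedure.** The hazards are stated without a site limit: "If volunteers have a metal implant or foreign object in your body, the object could be displaced by the magnetic field", and "There can be increased heating near metal structures". The rule follows: "If volunteers have any implants in their body, they will inform the researcher conducting this study, and they will not be eligible". The same section lists the anterolateral thigh among the donor sites to be imaged.
- **Adverse Events.** Heating is described at or near "metallic objects embedded in body. However, these subjects will be excluded from participating this study by the use of the MRI Safety Screening Form". On powered devices it adds: "According to our exclusion criteria, all subjects with any type of activatable implants will be excluded from participating this study".

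Consent Procedures says that, once the consent and safety screening forms are collected, staff decide eligibility by the criteria set out earlier in the protocol. Recruitment says that all participants are screened before they enter the MRI environment.

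**The concern.** The list by which eligibility is decided is narrower than the safety statements made elsewhere in the same document. For a passive metal implant outside the torso, the metal item does not exclude and the other two sections do. Staff who work from the list alone could reach a different answer from staff who work from the procedure text. The protocol itself names displacement and heating as the hazards, and neither is confined to the torso. The restriction also does not fit the imaging plan, because metal in a thigh that is being imaged lies outside the item.

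What is at stake is a consistent safety rule at enrolment, not a statistical property of the study.

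**Working it through.** The protocol gives no figure on this point, so the check is a comparison of texts.

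**Step 1. Apply each section to the same cases.**

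| Case | Metal item, Subject Selection Criteria | MRI Procedure section | Adverse Events |
|---|---|---|---|
| Passive metal implant, torso | Excluded | Ineligible | Excluded |
| Passive metal implant, limb | Not reached | Ineligible | Excluded |
| Metallic foreign object, torso | Excluded | Hazard named, no ineligibility rule | Excluded |
| Metallic foreign object, limb | Not reached | Hazard named, no ineligibility rule | Excluded |
| Activatable implant, any site | Excluded by its own item | Ineligible | Excluded |

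The sections part company in the two limb rows. For implants, both other sections are stricter than the list. For foreign objects, only Adverse Events is, because the ineligibility sentence in the MRI Procedure section speaks of implants alone.

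**Step 2. See whether other items close the gap.** Three have no torso limit and bear on metal elsewhere: metal workers and machinists (fragments near the eyes), severe car accident victims, and tattoos that may contain metallic colouring. They reach some people with metal outside the torso. They do not reach someone with, say, a leg implant from planned surgery. The coverage is partial.

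**Step 3. See which text decides.** Consent Procedures points back to the inclusion and exclusion criteria. The only section set out as such a list is Subject Selection Criteria. Adverse Events comes after Consent Procedures, so its statement is not among the earlier criteria. It also assigns the exclusion to the screening form, whose content is not in the protocol.

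**Step 4. See whether the result depends on what volunteer means.** If the word is loose and covers everyone, the list and the MRI Procedure rule both apply to all subjects, and the limb rows conflict for all. If it means only the non-patient cohort, the same conflict remains for that cohort, and for patients only Adverse Events states a whole-body rule. The site conflict survives either way.

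**The case against.** The best defence is that the texts add up rather than collide. The list never says that metal outside the torso is allowed, so staff can follow all three sections by applying the strictest. The ineligibility sentence in the MRI Procedure section also stands earlier than Consent Procedures. Everyone is screened, and the form is completed before eligibility is settled. This stands as to risk and is why the point is minor. It does not make the list agree with the rest, and the unseen form cannot be assumed to supply the missing rule.

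The sponsor could also reconcile the text the other way, by keeping the torso limit and changing the other two sections. That is open to it, but the protocol already commits to the broader exclusion in two places.

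Two stronger readings are tempting, and the documents do not support them.

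- **That clinical patients fall outside the safety list.** The lead-in says volunteer, and Design Overview plans 25 volunteers and 50 patients, so a literal reader might infer that 50/(25 + 50), or two-thirds of the evaluable subjects, are not covered. Design Overview, Recruitment and Compensation do use the word for the non-patient cohort, as in "Volunteer subjects will not be compensated for their participation". But the MRI Procedure section uses it for whoever is in the scanner, Consent Procedures uses it interchangeably with subject, and Adverse Events says that the exclusion criteria cover all subjects with activatable implants. Loose usage is the likelier explanation, and a wording clarification is all that it warrants.
- **That a share of sites or subjects is exposed.** The anterolateral thigh is one of five named donor sites, but that list is expressly open-ended, so no proportion of sites, scans or people follows from it.

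**Conclusion.** The inconsistency on body site is real and of minor severity. The metal item in Subject Selection Criteria stops at the torso. The MRI Procedure section (for implants) and Adverse Events (for embedded metallic objects) set no site limit. The protocol does not say how many people have passive metal outside the torso, so no count is given, and nothing shows that anyone would be scanned unscreened. Analysis and sample size are unaffected.

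The conclusion rests on reading the reference in Consent Procedures as pointing to Subject Selection Criteria. It does not depend on how volunteer is read. Whether any gap exists in practice depends on the screening form, which is not shown.

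**What to change.** In Subject Selection Criteria, delete the torso restriction from the passive-metal item so that it matches the MRI Procedure and Adverse Events sections, and confirm that the MRI Safety Screening Form applies the same rule. In the same amendment, reword the lead-in so that the MR-safety items apply to any subject, in line with Adverse Events.

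The cost is two phrase edits and a check of one form. The drawback is a slightly narrower eligible pool, since people with metal in a limb whom the item does not now exclude would be excluded by the list itself. The protocol gives no figure for that loss, but its other sections already turn most of these people away.
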